Appendix 2. Pediatric Early Warning Score

Appendix 3. Programming Specifications

1) If the age from the Day 1 eCRF is not available, age will be calculated as follows:

Only year is provided for the date of birth (DOB). Use July 1 for the month and day.

- a) AGE (years) is calculated from the number of days between the DOB and Study Day 1,
- b) Use the SAS INTCK function to determine the number of "1st-of-month days" (eg, January 1st, February 1st, March 1st) between DOB and Day 1 (inclusive),
- c) Divide the result in (b) by 12, AGE = the integer of the result in (c), Age for laboratory test reference range will be based on the age at the sample collection date.
- 2) All screened participants refer to all participants who are screened (ie, with non-missing screening date) and have a screening number. For summaries the same participant is counted only once.
- 3) Screen failure participants are the participants who were screened and answered "No" for any inclusion criteria or "Yes" for any exclusion criteria regardless of which version of protocol the participant was consented to.
- 4) Participants in the All Enrolled Analysis Set are defined as participants enrolled into the study. IXRSRAND is the source to determine whether the participants is enrolled (ie, participant with non-missing ENRDTN in the IXRSRAND dataset), and confirmed by the eCRF ENROLL dataset (ie, ENROLLYN = "Yes" in ENROLL dataset).
- 5) Enrolled treatment (ie, TRT01P in ADSL) is derived from IXRSRAND, while actual treatment received (ie, TRT01A in ADSL) is assigned as the enrolled treatment if the participant took at least 1 dose of study drug and assigned as blank if the participant was never dosed.
- 6) In the disposition table, the reasons for premature discontinuation are displayed in the order as they appear on the eCRF.
- 7) Body mass index (BMI)

BMI will be calculated only at baseline as follows:

- BMI = (weight [kg]) / (height [meters]²)

Baseline height and weight will be used for this calculation if available.

8) Details of additional COVID-19 medications are provided in table below.

Drug name	ATC Code	WHODRUG Preferred Term
Chloroquine	P01BA	CHLOROQUINE
Hydroxychloroquine	P01BA	HYDROXYCHLOROQUINE
Lopinavir/ritonavir	J05AR	LOPINAVIR/RITONAVIR
Ribavirin	J05AP	RIBAVIRIN
Bamlanivimab/Etesevimab		BAMLANIVIMAB/ETESEVIMAB
Casirivimab/Imdevimab		CASIRIVIMAB/IMDEVIMAB
Molnupiravir		MOLNUPIRAVIR

Table 13-1.Additional COVID-19 Medications

ATC = anatomical therapeutic chemical

Additional medications may be included during final review of concomitant medications prior to data finalization.

9)	Grouping on	COVID-19	medications	other than	the study drug
- /					

Table 13-2.Grouping on the COVID-19 Medications other than the Study Drug

Standardized Medication Name	Experimental antiviral	Immune modulator	Anti- inflammatory	AntiViral antibody therapy	Other medication
ANAKINRA	N	Y	Y	N	Ν
AZITHROMYCIN	Y	Y	Y	N	Ν
BETAMETHASONE	N	Y	Y	N	Ν
CLARITHROMYCIN	N	N	Y	N	N
CYCLOBENZAPRINE	N	Ν	N	N	Y
DEXAMETHASONE	N	Y	Y	N	Ν
DEXAMETHASONE SODIUM PHOSPHATE	N	Y	Y	N	N
DIPHENHYDRAMINE; ZINC ACETATE	N	Ν	N	N	Y
ENOXAPARIN	N	N	N	N	Y
ENOXAPARIN SODIUM	N	N	N	N	Y
GANCICLOVIR	Y	N	N	N	N
HYDROCORTISONE	N	Y	Y	N	Ν
HYDROCORTISONE SODIUM SUCCINATE	N	Y	Y	N	N

Standardized Medication Name	Experimental antiviral	Immune modulator	Anti- inflammatory	AntiViral antibody therapy	Other medication
HYDROXYCHLOROQUIN E	Y	Ν	Ν	N	Ν
IMMUNOGLOBULIN G HUMAN	N	Y	N	N	N
IMMUNOGLOBULIN HUMAN NORMAL	N	Y	N	N	Ν
IMMUNOGLOBULINS NOS	N	Y	N	Ν	Ν
LEVOFLOXACIN	N	Ν	Ν	Ν	Y
METHYLPREDNISOLONE	N	Y	Y	Ν	Ν
ONDANSETRON	N	N	N	N	Y
PLASMA	N	Ν	N	Y	Ν
POTASSIUM PHOSPHATE DIBASIC	Y	Y	Y	N	N
POTASSIUM PHOSPHATE DIBASIC;SODIUM PHOSPHATE	Y	Y	Y	Ν	Ν
PREDNISOLONE	N	Y	Y	N	Ν
PREDNISOLONE SODIUM PHOSPHATE	N	Y	Y	N	N
PREDNISONE	N	Y	Y	N	N
REMDESIVIR	N	N	N	N	Y
RITUXIMAB	N	Y	N	Ν	N
TOCILIZUMAB	N	Y	Y	N	N
ZINC	N	Ν	N	N	Y

Additional medications may be included during final review of COVID-19 medications other than the study drug prior to data finalization.

- 10) Graded Laboratory Abnormalities Summary
 - The following labels will be used for laboratory abnormalities and Grade 3 or 4 laboratory abnormalities summary tables and listings:

Battery	Lab Test Label Used in l-labtox Listing	Toxicity Direction	Lab Test Label Used in t-labtox Table
Hematology	Basophils	Increase	Basophils (Increased)
	Eosinophils	Increase	Eosinophils (Increased)
	Hemoglobin	Decrease	Hemoglobin (Decreased)
	Lymphocytes	Decrease	Lymphocytes (Decreased)
	Monocytes	Increase	Monocytes (Increased)
	Neutrophils	Decrease	Neutrophils (Decreased)
	Platelets	Decrease	Platelets (Decreased)
	WBC	Decrease	WBC (Decreased)
Chemistry	Albumin	Decrease	Albumin (Decreased)
	Alkaline Phosphatase	Increase	Alkaline Phosphatase (Increased)
	ALT	Increase	ALT (Increased)
	AST	Increase	AST (Increased)
	Calcium	Decrease	Calcium (Decreased)
	Calcium, Ionized	Decrease	Calcium, Ionized (Decreased)
	Creatine Kinase	Increase	Creatine Kinase (Increased)
	Creatinine	Increase	Creatinine (Increased)
	Direct Bilirubin	Increase	Direct Bilirubin (Increased)
	eGFR, Bedside Schwartz	Decrease	eGFR, Bedside Schwartz (Decreased)
	GGT	Increase	GGT (Increased)
	Magnesium	Decrease	Magnesium (Hypomagnesemia)
	Serum Carbon Dioxide	Decrease	Serum Carbon Dioxide (Decreased)
	Serum Glucose	Increase	Serum Glucose (Hyperglycemia)
	Serum Glucose	Decrease	Serum Glucose (Hypoglycemia)
	Serum Potassium	Increase	Serum Potassium (Hyperkalemia)
	Serum Potassium	Decrease	Serum Potassium (Hypokalemia)
	Serum Sodium	Increase	Serum Sodium (Hypernatremia)
	Serum Sodium	Decrease	Serum Sodium (Hyponatremia)
	Total Bilirubin	Increase	Total Bilirubin (Hyperbilirubinemia)
	Urea Nitrogen (BUN)	Increase	Urea Nitrogen (Increased)
Coagulation	Prothrombin Time	Increase	Prothrombin Time (Increased)

Battery	Lab Test Label Used in l-labtox Listing	Toxicity Direction	Lab Test Label Used in t-labtox Table
	Activated Partial Thromboplastin Time	Increase	Activated Partial Thromboplastin Time (Increased)
	Prothrombin Intl. Normalized Ratio	Increase	Prothrombin Intl. Normalized Ratio (Increased)
Urinalysis	Urine Glucose	Increase	Urine Glucose (Glycosuria)
	Urine Protein	Increase	Urine Protein (Proteinuria)

11) Lab and blood pressure evaluation

Test	Evaluation
globulin	globulin in $g/dL = Total$ Protein in $g/dL - Albumin$ in g/dL
albumin: globulin (A:G) ratio	A:G (%) = Albumin in g/dL / (Total Protein in g/dL – Albumin in g/dL)
BUN to Creatinine ratio (%)	BUN: SCr (%) = BUN/ SCr, where BUN is Blood Urea Nitrogen (mg/dL); Cr is Creatinine (mg/dL)
eGFR (Bedside IDMS-traceable Schwartz GFR Calculator for Children)	GFR (mL/min/1.73 m ²) = (0.413 × Height in cm) / Creatinine in mg/dL
mean arterial pressure (MAP)	mean arterial pressure = diastolic pressure + $(1/3) \times$ pulse pressure, where pulse pressure = systolic pressure – diastolic pressure.

12) Confidence Interval (CI) for Single Proportion

 The 95% CI for percentage estimate is calculated based on the Clopper-Pearson exact method.
 proc freq;

```
proc freq;
by cohort;
tables event/ binomial alpha=0.05;
exact binomial;
output out=_ci95 binomial;
run;
```

13) TEAE

Events with Missing Onset Day and/or Month

An event is considered treatment emergent if the following 3 criteria are met:

a) The month and year (or year) of onset date is the same as or after the month and year (or year) of the first dose of study drug, and

- b) The month and year (or year) of the onset date is the same as or before the month and year (or year) of the 30th day after the date of the last dose of study drug, and
- c) End date is as follows: The (complete) end date is on or after the first dose date, or The month and year (or year) of end date is the same or after the month and year (or year) of the first dose of study drug, or End date is completely missing

Events with Completely Missing Onset Date

• An AE with a completely missing onset date is defined as TEAE if end date meets any of the 3 criteria specified above.

14) The precision in reporting numerical values should be as follows:

- Raw measurements will be reported the same as the data captured electronically or on the eCRF.
- Standard deviation and standard error will be reported to one more significant decimal place than the raw measurement.
- Mean, median, minimum, Q1, Q3, maximum, 95% CIs will be reported to the same number of decimal places of the raw measurements.
- Exceptions may be considered; for example, if more than 4 significant digits are provided for the measurement.
- 15) Last dose date is not expected to be missing. However, if last dose date is missing due to data issues, it will be imputed using the maximum of non-missing, non-zero dose, study drug start and stop dates.

16) Ordinal scale and oxygen support status

• The Ordinal Scale is an assessment of the clinical status of a given study day. Each day, the worst (ie, lowest ordinal) score from the previous day will be recorded (ie, on Day 3, the lowest ordinal score from Day 2 is obtained and recorded for Day 2). The original Ordinal Scale (A to G) has been converted to a 7-point scale with the associated oxygen support status defined in the following table:

Ordinal Scale		Oxygen Support Status	
1	Death	Death	
2	Hospitalized, on invasive mechanical ventilation or ECMO	Invasive Mechanical Ventilation	
3	Hospitalized, on non-invasive ventilation or high flow oxygen devices	High Flow Oxygen	
4	Hospitalized, requiring low flow supplemental oxygen	Low Flow Oxygen	
5	Hospitalized, not requiring supplemental oxygen - requiring ongoing medical care (COVID-19 related or otherwise)	Room Air	
6	Hospitalized, not requiring supplemental oxygen - no longer requires ongoing medical care (other than per protocol RDV administration)	Room Air	
7	Not hospitalized	Discharge	

17) Censoring rules for competing risk analysis

- Time to ≥ 2 point improvement and time to ≥ 1 point improvement: if a participant did not experience the event of interest and did not die, the participant was censored at the last non-missing assessment date. Participants who died were considered to have experienced a competing event.
- Time to recovery: Participants not achieving recovery at the last assessment were censored on the day of the last assessment. Participants who died were considered to have experienced a competing event.
- Time to discharge from hospital: Participants not discharge at the last assessment were censored on the day of the last clinical assessment. Participants who died were considered to have experienced a competing event.

18) Details on the LOQ and LOD for the viral load samples are provided below.

Table 13-3.Viral Load Sample Details

Sample type	Limit of quantitation (copies/mL)	Limit of detection (copies/mL)
Nasal/oropharyngeal samples Nasopharyngeal/oropharyngeal samples ET aspirates	1018	925
Rectal or fecal swabs	488	306

- 19) Quantitative and categorical summary on SARS-CoV2 results and change from baseline in SARS-CoV-2 viral load up to Day 10 or up to the first confirmed negative PCR result (whichever comes first)
 - For quantitative summary (e.g., mean viral load, change from baseline etc.), "Inconclusive" SARS-CoV2 result is set to missing
 - For categorical SARS-CoV2 summary, 3 categories will be included, i.e. Positive, Inconclusive, Negative
 - Positive = Any numeric result or "< 1018cp/mL SARS-CoV-2 detected" (for Nasal/oropharyngeal samples, Nasopharyngeal/oropharyngeal samples, or ET aspirates) or "< 488cp/mL SARS-CoV-2 detected" (for rectal or fecal swabs)
 - Negative = "No SARS-CoV2 detected"
 - Inconclusive = "Inconclusive"

20) Days to the first confirmed negative PCR result

- Categorical SARS-CoV2 and SARS-CoV2 negative summary will be separated out by sample type. There will be no combined positive or negative category using 2 or 3 sample types.
- Confirmed negative PCR result is defined as 2 consecutive negative results, or negative at last available sample for participants who completed or discontinued from study. Notice 2 negative results from the same day do not equal confirmation.
- For a negative SARS-CoV2 confirmation, "Inconclusive" SARS-CoV2 result will not be considered as missing thus a "Negative" followed by a "Inconclusive" is NOT a confirmed negative PCR result.
- All participants without a confirmed SARS-CoV2 negative result will be censored on the last day with available PCR test results.

GS-US-540-5823_SAP_v1.0_Final_Cohorts_1_to_8

ELECTRONIC SIGNATURES

Signed by	Meaning of Signature	Server Date (dd-MMM- yyyy hh:mm:ss)
PPD	Biostatistics eSigned	22-May-2023 11:23:50
PPD	Global Development Lead (GDL) eSigned	22-May-2023 18:13:26
PPD	Clinical Pharmacology eSigned	24-May-2023 14:33:01

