1.3. Sample Size and Power

The total sample size will be at least 52 participants.

Twelve (12) participants for each cohort (Cohorts 1-4) will be enrolled in this study. Pharmacokinetic data from these participants will provide >99% power for each cohort to conclude exposure equivalence of RDV AUC_{tau} in adolescents and children vs. 25 healthy adult participants in GS-US-399-5505 study (see Table 1-2) using two one-sided tests with each performed at an alpha level of 0.05. In this power analysis, it is assumed that the expected geometric mean ratio of AUC_{tau} between the adolescents and children group vs. the adult group is equal to 1, the inter-participant standard deviation (SD) (natural log scale) of AUC_{tau} is 0.18, and the equivalency boundary is 70% to 143%.

Meanwhile, twelve (12) participants from each cohort (Cohorts 1-4) will also provide >99% power to conclude exposure equivalence of RDV C_{max} in adolescents and children, compared to 26 healthy adult participants in GS-US-399-5505 study (see Table 1-2), assuming the expected geometric mean ratio of C_{max} between the adolescents and children group and the adult group is equal to 1, the inter-participant SD (natural log scale) of C_{max} is 0.19, and the equivalency boundary is 70% to 143%.

Sample size and power calculations were made using the software package nQuery Advisor(R) Version 8.5.

Table 1-2. Remdesivir, Nucleoside Metabolite GS-441524, and GS-704277 Plasma PK Parameters by Dose Following 30-Minute IV Infusion(s) of Remdesivir in Healthy Adult Participants in GS-US-399-5505

Study	GS-US-399-5505			
	Multiple RDV Dose (100mg)			
PK Parameter ^a		Day 5 and 10		
		$N = 26^{b}$		
Plasma RDV	Remdesivir	GS-441524 Metabolite	GS-704277 Metabolite	
C _{max} (ng/mL)	2228.8 (19.2)	145.0 (19.3)	245.5 (33.9)	
C _{tau} (ng/mL)		69.2 (18.2)		
C _{last} (ng/mL)	8.1 (46.9)	12.2 (50.0)	3.9 (27.5)	
T _{max} (h)	0.68 (0.25, 0.75)	1.51 (1.50, 2.00)	0.75 (0.75, 0.78)	
T _{last} (h)	4.00 (4.00, 4.02)	96.00 (96.00, 96.00)	8.00 (8.00, 8.00)	
t _{1/2} (h) ^d	0.96 (0.86, 1.08)	27.36 (25.29, 30.32)	1.23 (1.15, 1.38)	
AUC _{last} (h·ng/mL)	1562.8 (17.0)	4189.3 (17.7)	454.4 (31.8)	
AUC _{tau} (h·ng/mL)	1585.3 (16.6)	2229.2 (18.4)	461.5 (31.4)	
CL _{ss} (mL/h)	65068.7 (19.8)			
V _z (mL)	92557.2 (29.5)			

% CV = percentage coefficient of variation; IV = intravenous; PK = pharmacokinetic; Q1 = first quartile; Q3 = third quartile; $RDV = remdesivir (GS-5734^{TM})$

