7.4.3. COVID-19 Medications Other Than the Study Drug

COVID-19 medications from the first day of first dose of study drug administration until the end of the study will be categorized into the following categories:

- Experimental antiviral
- Immune modulator
- Anti-inflammatory
- Antiviral antibody therapy
- Other medication

Refer to Table 13-1 for the list of COVID-19 medications and the associated categories. It should be noted that a COVID-19 medication may belong to more than one category.

One of the secondary endpoints is the proportion of participants with concomitant use of medications other than RDV for treatment of COVID-19. Therefore, a summary table will present the number and percentages of participants with concomitant use of COVID-19 medications by cohort and overall for the Safety Analysis Set, sorted first by categories and then by PT in descending order of total frequency.

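### Table 13-2 flags two potassium phosphate entries as antiviral, immune modulator and anti-inflammatory, at odds with its other mineral and supportive entries, so class rows of the Section 7.4.3 summary can be misstated

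*SAP*

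**What the plan says.** Section 7.4.3 sets up five medication classes: experimental antiviral, immune modulator, anti-inflammatory, antiviral antibody therapy and other. It states the purpose: "One of the secondary endpoints is the proportion of participants with concomitant use of medications other than RDV for treatment of COVID-19". For that endpoint, "a summary table will present the number and percentages of participants with concomitant use of COVID-19 medications by cohort and overall", on the Safety Analysis Set, "sorted first by categories and then by PT in descending order of total frequency". One drug may count in several classes: "It should be noted that a COVID-19 medication may belong to more than one category".

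The assignment of drugs to classes is in Appendix 3, item 9, Table 13-2, titled "Grouping on the COVID-19 Medications other than the Study Drug". Two of its rows, "POTASSIUM PHOSPHATE DIBASIC" and "POTASSIUM PHOSPHATE DIBASIC;SODIUM PHOSPHATE", carry Y for Experimental antiviral, Immune modulator and Anti-inflammatory, and N for Antiviral antibody therapy and Other medication. A note under the table allows further medications to be included at final review. It says nothing about revising flags already set.

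Section 7.4.3 refers the reader to Table 13-1 for the list of medications and their categories. Table 13-1 has columns for drug name, ATC code and preferred term, but none for category.

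**The concern.** The two phosphate rows do not fit the rest of the table. Its other mineral entries (zinc, and diphenhydramine with zinc acetate) and its supportive agents (such as ondansetron and enoxaparin) are Other only. Dexamethasone and tocilizumab get two classes, and ganciclovir and hydroxychloroquine get one. The two phosphate entries get three, and the SAP does not explain why.

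In a single-arm study with no formal testing, the class breakdown is where a reader sees how much other COVID-19 treatment was given alongside remdesivir. If the lookup is programmed as it stands, a participant whose only listed medication is one of these two entries appears under three treatment classes. The Experimental antiviral row is the most exposed, because few other medications are listed there.

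**Working it through.** The SAP states no figure to reproduce. The check is a recount of Table 13-2, followed by the weight of one participant.

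**Step 1: pattern.** Table 13-2 has 30 rows. Reading the five flags in column order, exactly three rows are Y Y Y N N: azithromycin and the two phosphate rows. Both phosphate rows are complete in the text and line up with the column headings.

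**Step 2: share of each class.** Rows flagged Y, with and without the two phosphate rows:

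| Class | As written | Without phosphate | Phosphate share |
|---|---|---|---|
| Experimental antiviral | 5 | 3 | 2 of 5 |
| Immune modulator | 18 | 16 | 2 of 18 |
| Anti-inflammatory | 15 | 13 | 2 of 15 |
| Antiviral antibody therapy | 1 | 1 | 0 |
| Other medication | 8 | 8 | 0 |

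The three other Experimental antiviral rows are azithromycin, ganciclovir and hydroxychloroquine. If both phosphate rows moved to Other medication, that class would rise from 8 to 10 rows.

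**Step 3: weight of one user.** The summary counts participants, so one user changes a class percentage by 100/n if not already counted in that class, and by 0 otherwise. The denominators come from Section 1.3: "Twelve (12) participants for each cohort (Cohorts 1-4) will be enrolled in this study", and a total of at least 52.

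- Cohort of 12: 100/12 = 8.3 percentage points.
- Overall: 100/52 = 1.9 percentage points. Because 52 is the minimum enrolment, this is a ceiling; a larger total gives a smaller figure.

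Both figures take every enrolled participant as dosed, since the summary uses the Safety Analysis Set.

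**Step 4: reach.** The any-COVID-19-medication proportion counts a participant with at least one listed drug. Moving the two rows to Other medication leaves every such participant counted, so the proportion does not move. Deleting the rows lowers it only for participants with no other listed drug. The viral load exclusion in Section 3.7 works from Table 13-1, which does not list potassium phosphate. Section 3.3 puts no covariates in the efficacy analyses.

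**The case against.** The case for treating this as small has several parts.

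- **Overlap.** Sixteen other rows are Immune modulator and 13 are Anti-inflammatory, including the corticosteroids and tocilizumab. A phosphate user who also received one of these adds nothing to those totals. This stands: it is wrong to infer that every user adds one count to all three classes. The overlap gives less protection in the Experimental antiviral class, with only three other rows.
- **Visibility.** The table prints preferred terms within class, so a reader could see potassium phosphate listed and discount it. This is true of the term rows, but the class percentages would still include it.
- **Multiple membership.** Section 7.4.3 allows a drug to sit in several classes. That permits more than one flag; it does not explain these three.
- **Cause.** A reader might infer that the product was electrolyte replacement, or that the azithromycin flags were copied into the wrong rows. The SAP gives no indication for use, and the first column holds a standardized medication name. Either the flags or the name could be wrong, and the match with azithromycin does not settle which. This stands, and it means the rows should not be recoded without looking at the source records.
- **Confounding.** A reader might infer that efficacy results are distorted. The documents do not support that, because no efficacy analysis draws on Table 13-2.

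**Conclusion.** The two rows are inconsistent with the table that contains them, and nothing in the SAP justifies their flags. Programmed as written, they can misstate three class rows in one descriptive summary of a secondary endpoint. For each user with no other drug in the class, the size is 8.3 points in a cohort of 12 and at most 1.9 points overall.

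The number of users is unknown. That the list was compiled from medications actually reported, so that at least one participant is affected, is an assumption; the net effect could be nil. A reader might also infer that the headline proportion of participants on any COVID-19 medication is inflated. That would follow only if the product was not given for COVID-19, and only for participants with no other listed drug. What is at stake is the accuracy of a descriptive report, not inference. It is worth correcting because the class breakdown is part of the planned output and the correction is cheap.

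**What to change.** 1. Check both rows against the reported medication term and indication.
2. If the standardized name is right, recode both rows to N N N N Y, or delete them if the product was not given for COVID-19. If the name is a dictionary-coding error, correct the name and set the flags that belong to the corrected drug.
3. In Section 7.4.3, cite Table 13-2 instead of Table 13-1 for the categories.
4. Produce the Section 7.4.3 summary from the corrected mapping. Record the change in the clinical study report, as Section 1 of the SAP requires for changes after finalization.

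The cost is a check of the source records for two entries, two rows of a lookup table, one cross-reference and one table run.
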